### 7.9 OTHER ANALYSES

Analysis of potential withdrawal effects based on PWC-20 assessments  Change in withdrawal symptoms based on PWC-20 will be analysed descriptively.

# 8. TIMEPOINT OF RELEASE OF TREATMENT INFORMATION

The treatment information will be released to unblind the trial database after the last patient has completed their End-of-Study/Follow-up visit and all data has been entered and cleaned as defined in the "Data Ready to be Unblinded and/or Final Trial Closure Notification" (RUN) form.

### 10. ADDITIONAL SECTIONS

# 10.1 DETAILED DESCRIPTION OF MCCB MISSING DATA HANDLING AND IMPUTATION

All imputations will be carried out separately for each study visit since there may be differences in test performance at different time points.

For the domains of Working Memory (consisting Letter-Number Span test and Wechsler Memory Scale 3rd ed. Spatial Span subtest) and Speed of Processing (consisting Trail Making Test Part A, Brief Assessment of Cognition in Schizophrenia – Symbol Coding subtest, and Category Fluency test – animal naming), if one of the component test items has missing value at a visit, the corresponding domain score can still be derived using the observed raw scores of the remaining test items in that domain for that visit. If more than one of the component test items have missing value at a visit, the corresponding domain score is missing at that visit.

For the other five domains (Verbal Learning, Reasoning and Problem Solving, Visual Learning, Attention / Vigilance, and Social Cognition) which have only one test item, if the test item has missing value at a visit, the corresponding domain score is missing.

The following describes the derivation of composite T-scores from a partially assessed MCCB.

For Visit 1 assessments, at least two-thirds of the cognitive domains (i.e., a minimum of five out of the seven domains for the MCCB overall composite score and a minimum of four out of the six domains for the MCCB neurocognitive composite score) need to be successfully assessed for it to be counted as an assessment occasion with non-missing value.

For assessments from Visit 2 and onward, at least half of the domains (i.e., a minimum of four out of the seven domains for the MCCB overall composite score and a minimum of three out of the six domains for the MCCB neurocognitive composite score) need to be successfully assessed for it to be considered an assessment occasion with non-missing value.

If an individual test score is missing at a visit, the missing T-score of this test item is imputed using the following algorithm:

$$\hat{T}_{ijk} = \bar{T}_{ij+} + \bar{T}_{i+k} - \bar{T}_{i++}$$

where  $\widehat{T}_{ijk}$  is the missing T-score at Visit i to be imputed for test j of subject k

 $\bar{T}_{ij+}$  is the mean T-score at Visit i on test j from all subjects

 $\bar{T}_{i+k}$  is the mean T-score at Visit i on all available tests from subject k

 $\bar{T}_{i++}$  is the mean T-score at Visit *i* of all available tests from all subjects.

In order to produce a more plausible imputed value that reflects the naturally occurring variability around the measure of a subject's cognitive ability, a small amount of random variance will be added to each predicted value  $\hat{T}_{ijk}$ . The final imputed T-score of the missing test item would become:

$$\tilde{T}_{ijk} = \hat{T}_{ijk} + s_i * Z$$

where Z is a random draw from the standard normal distribution, and  $s_i$  is the visit specific residual standard error from a multiple regression model of the observed test T-score  $(T_{ijk})$  on the average T-score  $(T_{ij+})$  across patients of test j and the average T-score  $(T_{i+k})$  of patient k across the 10 tests, based on only data from Visit i.

This will not only preserve the independent nature of the collected data, but also prevent exaggerating the precision of the treatment differences (9).

The test item T-score from the additive method above is then converted back to the raw score using the age and gender corrected "Normative Tables" in Appendix C of the MCCB Manual. The set of imputed and observed raw test item scores are then entered into the MCCB scoring program to calculate the composite T-scores.

When the test item T-score from the additive method cannot be mapped exactly to a raw score per the Normative Tables, the closest raw score will be used. In case of a tie when the test item T-score falls halfway between 2 closest values, the raw score that corresponds to the higher T-score is used.

Note that the imputed domain and test item T-scores here only serve as an intermediate step when deriving the composite T-scores. They will not be retained as the endpoints for the analyses of domain and test item T-scores.

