7.2 PLANNED ANALYSES

7.2.1 General considerations

The following patient analysis sets are defined for this trial:

- Randomized Set (RS): includes all patients who signed informed consent and were randomized into the trial, regardless if a patient was treated with trial medication. The RS is used for efficacy analyses and patients in RS are analysed under the randomized trial medication. Patients randomized in error and discontinued from the study before the start of trial medication will be excluded from the RS.
- Treated Set (TS): includes all patients who signed informed consent and were treated with at least one dose of the trial medication. Patients in TS are analysed under the actual trial medication received at randomization. The TS is used for safety analyses as well as demographics and baseline characteristics.

Data from patients who were screened but not randomized will be listed but not included in any summary or inferential statistics.

Page 80 of 112

Proprietary confidential information © 2023 Boehringer Ingelheim International GmbH or one or more of its affiliated companies

In general, baseline values are the measurements taken prior to the first administration of trial medication at randomization (Visit 2), or Visit 1a if no measurements are planned at Visit 2, (see Flow Chart). Further details will be provided in the TSAP.

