7.3 HANDLING OF MISSING DATA

Every effort will be made to collect complete data at the specific time points, even for patients who terminated trial medication prematurely. If not specified otherwise, missing data are not imputed and remain missing. Potential outliers will be reported and analysed as observed.

For the primary estimand analysis of the primary efficacy endpoint using the mixed strategy for handling intercurrent events, if a patient misses a visit, the missing data will not be imputed. The MMRM analysis will handle missing data based on a likelihood method under the "missing at random" assumption.

MCCB endpoints

All imputations will be carried out separately for each study visit since there may be differences in test performance at different time points.

For the domains of Working Memory (consisting Letter-Number Span test and Wechsler Memory Scale 3rd ed. Spatial Span subtest) and the Speed of Processing (consisting Trail Making Test Part A, Brief Assessment of Cognition in Schizophrenia – Symbol Coding subtest, and Category Fluency test – animal naming), if only one of the tests consisting of a domain has missing value at a visit, the corresponding domain score can still be derived using the observed test raw score for that visit. If more than one of the tests consisting of a domain have missing value at a visit, the corresponding domain score is missing at that visit.

For the other five domains (Verbal Learning, Reasoning and Problem Solving, Visual Learning, Attention / Vigilance, and Social Cognition) which has only one test, if the test has missing value at a visit, the corresponding domain score is missing.

If a domain score is missing at a visit, the missing T-score of this domain can be imputed using the proprietary algorithm developed by MATRICS.

Page 85 of 112

Proprietary confidential information © 2023 Boehringer Ingelheim International GmbH or one or more of its affiliated companies

For baseline assessment, at least two-thirds of the cognitive domains (i.e., a minimum of five out of the seven domains for the MCCB overall composite score and a minimum of four out of the six domains for the MCCB neurocognitive composite score) need to be successfully assessed at baseline for it to be counted as a test occasion with non-missing baseline value.

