For post-baseline assessments, at least half of the domains (i.e., a minimum of four out of the seven domains for the MCCB overall composite score and a minimum of three out of the six domains for the MCCB neurocognitive composite score) need to be successfully assessed to be considered a test occasion with non-missing value.

SCoRS endpoints

For the 20-item SCoRS assessment, if six or more of the 20 items have missing response, which includes the response of "N/A", for a patient at a visit, then the SCoRS total score for that patient at that visit is missing. If five or less of the 20 items have missing response, which includes the response of "N/A", for a patient at a visit, then the item with missing response will be imputed first with the average of the non-missing item values for the patient at the visit, and then SCoRS total score for the patient at the visit will be derived as the sum of the non-missing item values and the imputed item values.

PRECIS endpoints

The PRECIS scale consisted of 28 items, among which the first 26 items are coming from six domains, i.e., memory, communication, self-control, executive function, attention and sharpness of though, and the last 2 items measure overall degree of bother associated with all domains. For the aforementioned six domains, the maximum numbers of items allowed to be missing within each domain are 3, 1, 0, 0, 3 and 0, respectively, so that each domain would have at least 3 non-missing items. Within each domain, if the number of missing items exceed its allowable value, then the corresponding domain score would be considered missing, otherwise, the domain score is calculated as the average of the non-missing items scores under the domain. The PRECIS total score is calculated when not more than 7 items are missing overall, and the total score is calculated as the average of the non-missing item scores of the first 26 items.

A detailed description of the PRECIS items, the corresponding domains and the minimum number of non-missing items required for the domain scores is provided in Table 5.1:2.

Additional details on the handling of missing data will be specified in the TSAP prior to unblinding.

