#### 3. INTRODUCTION

As per International Conference on Harmonisation (ICH) E9, the purpose of this document is to provide a more technical and detailed elaboration of the principal features of the analysis described in the protocol, and to include detailed procedures for executing the statistical analysis of the primary and secondary variables and other data.

This Trial Statistical Analysis Plan (TSAP) assumes familiarity with the Clinical Trial Protocol (CTP), including Protocol Amendments. In particular, the TSAP is based on the planned analysis specification as written in CTP Section 7 "Statistical Methods and Determination of Sample Size". Therefore, TSAP readers may consult the CTP for more background information on the study, e.g., on study objectives, study design and population, treatments, definition of measurements and variables, planning of sample size, randomization.

SAS® Version 9.4 will be used for all analyses if not otherwise specified. Pheonix WinNonlinTM Version 8.1 will be used for pharmacokinetic (PK) analyses.

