## 4. CHANGES IN THE PLANNED ANALYSIS OF THE STUDY

For the further endpoint of change from screening Visit 1a in PRECIS individual items and domain scores at Week 24, only the PRECIS domain scores will be analyzed, and the PRECIS individual items will not be analyzed.

Definition of baseline for the assessments of efficacy, and C-SSRS will include assessments up to but no later than the day of the first administration of study medication.

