#### 6.7 BASELINE, TIME WINDOWS AND CALCULATED VISITS

In general, baseline values are the measurements taken prior to the first administration of trial medication. For assessments of efficacy, and C-SSRS, baseline will be defined as the last available assessment performed at or before randomization (Visit 2), and no later than the day of the first administration of study medication. Assessments done at Visit 1 or Visit 1a can be used as baseline if Visit 2 assessment is not planned, not available, or invalid.

For MCCB, only the assessment performed at randomization (Visit 2), and no later than the day of the first administration of study medication will be used as the baseline. If no valid assessment is available at Visit 2 then baseline value will be missing; assessments performed at Visits 1 and 1a will not be used as baseline.

Tables in this section define the analysis visits and windows which will be used for the analyses of efficacy and safety endpoints. Actual study day will be calculated starting with the date of first administration of trial treatment as Day 1. Unscheduled assessments will be mapped to the analysis visits together with the scheduled assessments.

Inclusion of an assessment into mapping consideration will depend on its on-/off-treatment status and per specific estimand (i.e., off-treatment data will be included into mapping consideration only when the associated ICE is handled under the treatment policy approach). If more than one assessment falls into the same analysis visit window, the assessment

performed closest to the planned day will be selected for analyses. In case of a tie, the later assessment will be used.

Table 6.7: 1 Analysis visit windows for MCCB, VRFCAT, SCoRS,

Analysis Visit	Nominal Week	Planned Day	Actual Day Window
Baseline		1	≤1
Visit 6	Week 12	85	2 – 126
Visit 11	Week 26	183	≥127

Table 6.7: 2 Analysis visit windows for PRECIS,

Analysis Visit	Nominal Week	Planned Day	Actual Day Window
Baseline		1	≤1
Visit 7	Week 15	106	2 – 126
Visit 10	Week 24	169	≥127

Table 6.7: 3 Analysis visit windows for Tower of London,

Analysis Visit	Nominal Week	Planned Day	Actual Day Window
Baseline		1	≤1
Visit 11	Week 26	183	≥2
(for Tower of London,			

[figure not shown]

Table 6.7: 7 Analysis visit windows for clinical laboratory evaluations (on-treatment period)

Analysis Visit	Nominal Week	Planned Day	Actual Day Window
Baseline		1	≤1
Visit 2	Week 0 (post-baseline)	1	2 – 35
Visit 4	Week 6	43	36 – 77

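### Does the lower MCCB completeness threshold at Visit 2 in SAP 10.1 (4 of 7 domains, against 5 of 7 at baseline in Protocol 7.3) call for a change?

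*SAP*

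**What the plan says.** Protocol 7.3, under the MCCB endpoints, has two completeness rules for the overall composite. The stricter one reads "For baseline assessment, at least two-thirds of the cognitive domains (i.e., a minimum of five out of the seven domains"; the looser one reads "For post-baseline assessments, at least half of the domains (i.e., a minimum of four out of the seven domains". The neurocognitive composite has the parallel pair, 4 of 6 and 3 of 6. Protocol 7.2.1 locates baseline: "baseline values are the measurements taken prior to the first administration of trial medication at randomization (Visit 2", with Visit 1a as the alternative only where nothing is planned at Visit 2. The Flow Chart schedules the MCCB at Visit 2.

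SAP 10.1 keeps the same two fractions but ties them to visit numbers. The two-thirds rule opens with "For Visit 1 assessments, at least two-thirds of the cognitive domains", and the half rule with "For assessments from Visit 2 and onward, at least half of the domains (i.e., a minimum of four out of the seven domains". SAP 6.7 allows only the Visit 2 assessment as the MCCB baseline and adds that "assessments performed at Visits 1 and 1a will not be used as baseline".

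SAP Section 3 says that "the TSAP is based on the planned analysis specification as written in CTP Section 7". The visible text of SAP Section 4 lists two changes: PRECIS individual items are not analysed, and a timing limit is set, beginning "Definition of baseline for the assessments of efficacy, and C-SSRS will include assessments up to but no later than the day". Neither concerns the number of MCCB domains.

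**The concern.** Read together, these sections mean that the protocol's stricter rule covers no baseline value in the SAP. It survives only for Visit 1, whose score serves randomisation and the stratum. A Visit 2 record with exactly 4 of 7 domains is a missing baseline under the protocol and a valid one under the SAP.

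The baseline matters twice in the primary analysis: it is subtracted to form the change score, and it enters the MMRM as a covariate at each visit (SAP 7.4.1 and 10.2.1). SAP 6.7 gives no fallback when it is missing. It is a fair inference, though not stated in either document, that a patient without a baseline drops out of the model. The threshold could therefore decide who is analysed for the primary endpoint. Two written rules for that decision, with the difference not declared in the visible text, would normally invite the question of which one governs and whether the choice could be made after unblinding.

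**Working it through.** **1. Is either count an arithmetic slip?** Two-thirds of 7 is 4.67, rounded up to 5; two-thirds of 6 is 4; half of 7 is 3.5, rounded up to 4; half of 6 is 3. Every stated count matches its fraction. The documents differ only in the visit at which the looser rule begins.

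**2. How incomplete can an accepted baseline be?** Ten tests feed seven domains: Speed of Processing has 3, Working Memory has 2, and five domains have 1 each (Protocol Table 5.1:1). Under SAP 10.1 a multi-test domain survives one missing test and is lost with two or more. Enumerating all missing-test patterns:

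- exactly 5 domains present: 2 to 5 of the 10 tests missing;
- exactly 4 domains present: 3 to 6 of the 10 tests missing.

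In the worst case, the lower threshold therefore allows one more imputed test.

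**3. How many patients could be affected?** The documents give no rate. Assume that each test is missing independently with probability p. Then:

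- Speed of Processing is lost with probability a = 3p²(1−p) + p³;
- Working Memory is lost with probability b = p²;
- each single-test domain is lost with probability p.

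Exactly 4 of 7 means exactly three domains lost:

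P = 10p³(1−p)²(1−a)(1−b) + 10p²(1−p)³[a(1−b) + b(1−a)] + 5p(1−p)⁴ab

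For p = 5%: a = 0.00725 and b = 0.0025, so P = 0.001117 + 0.000208 + 0.000004 = 0.00133, and 586 × 0.00133 = 0.78.

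| p | P | Expected of 586 | Chance that nobody is affected, (1−P)^586 |
|---|---|---|---|
| 1% | 0.0000102 | 0.006 | 99% |
| 2% | 0.0000827 | 0.05 | 95% |
| 5% | 0.00133 | 0.8 | 46% |
| 10% | 0.01062 | 6.2 | 0.2% |

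A cruder calculation gives all seven domains one common missingness rate and ignores the protection that multi-test domains have: C(7,3)p³(1−p)⁴ × 586 = 0.02, 0.15, 2.1 and 13.5. That can serve as a pessimistic bound under independence.

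**4. What would excluding them do to power?** Protocol 7.5 uses a two-sample t-test with 220 evaluable patients per arm, standardised effect 0.35 and one-sided 0.025, and reports 95% power (95.6% in its simulations). Reproduced: the noncentrality is 0.35 × √(220/2) = 3.671 with 438 degrees of freedom, and power is 0.9557. At p = 10%, 220 × (1 − 0.01062) = 217.7 per arm and power is 0.9538. With the cruder count, 220 × (1 − 0.02296) = 214.9 per arm and power is 0.9516.

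**5. Could the choice of threshold bias the contrast?** All Visit 2 assessments are completed before the first dose (Protocol 4.1.4 and Flow Chart footnote 9), in a double-blind trial. The number of domains assessed at Visit 2 therefore cannot be an effect of treatment. Either threshold acts on a pre-treatment quantity in the same way in both arms.

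**The case for a change.** The strongest case for acting is that SAP Section 4 exists to record departures from the protocol. It records one to a further endpoint and one to the timing of baseline. A lower completeness threshold for the primary endpoint's baseline belongs there by the same standard. Protocol 7.3 does leave further missing-data detail to the TSAP, but replacing a stated number is more than adding detail. A sentence costs nothing, and without it a reader cannot tell whether the shift was intended.

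The point about the record stands, as far as the visible text goes. Section 4 has a redaction gap, and the MCCB Manual, which SAP 6.6 says governs missing tests, was not available, so a reason may exist out of sight. Whether the shift was deliberate cannot be settled from the documents. SAP 10.1 does rewrite this part in some depth: it names visits in place of baseline and post-baseline, and gives an explicit formula where the protocol cites a proprietary algorithm.

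The step from an undeclared difference to a defect in the analysis does not stand. The final SAP leaves the analyst one rule, fixed in writing, and SAP Section 8 places the release of treatment codes after data cleaning. Either threshold would be acceptable, and declaring the SAP's own would leave the analysis as it is.

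There is a mild trade-off. Accepting 4 of 7 keeps a randomised patient in the model with a baseline that rests on more imputed tests. Requiring 5 of 7 gives a better-measured baseline and may lose the patient. Neither is clearly superior.

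**Conclusion.** The documents do disagree: 5 of 7 domains (4 of 6 neurocognitive) at baseline in Protocol 7.3, against 4 of 7 (3 of 6) at Visit 2 in SAP 10.1. This is a point of record at the lowest level and not a weakness of the primary analysis.

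For the overall composite it touches only patients with exactly 4 of 7 domains at Visit 2. Under independent test-level missingness of 1% to 10%, that is about 0.006 to 6 of 586, and the largest power change is from 0.956 to 0.954. Those rates and the independence are assumptions; missing tests that cluster within patients could raise the count. The upper rates look pessimistic, because the MCCB comes first among the Visit 2 efficacy assessments (Protocol 6.2.3.1) and patients without a Visit 1 MCCB score are excluded (Protocol 3.3.3, criterion 25).

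Because the SAP rule can be followed as written, acts before treatment, and shows no bias or meaningful loss against the alternative, no change to the plan follows.

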### 10.2 COMPUTATIONAL DETAILS OF THE MMRM ANALYSIS

### 10.2.1 Example SAS code for the primary analysis by MMRM:

[figure not shown]
```
PROC MIXED DATA=indata cl method=reml covtest;
    CLASS strata visit trt subject;
    MODEL ept = strata visit|trt base|visit / ddfm=kr s CL;
    REPEATED visit / subject= subject type=un r rcorr;
    LSMEANS visit*trt / pdiff=all om cl alpha=0.05 slice=visit;
RUN;
```

[figure not shown]
### 10.2.2 Methods to overcome non-convergence issues of MMRM analyses

[figure not shown]
In the event of non-convergence, the following methods will be attempted (in order) to overcome the issue:

[figure not shown]
1. Add the 'singular=1e-10' option in the model statement – this raises the threshold at which columns are declared linearly dependent (from typically 1e-12).

[figure not shown]
- 2. Set 'maxiter=100' in the PROC MIXED statement this increases the number of convergence iterations used from a default of 50.
- 3. Set 'scoring=4' to specify use of the Fisher scoring algorithm in the first 4 iterations.
- 4. Include the statement 'performance nothread' this removes multi-threading from the calculations.

### 10.7 CONCOMITANT THERAPIES OF SPECIAL INTEREST

Table 10.7: 1 Concomitant therapies of special interest by ATC classifications or WHO DD preferred names

Category	Subcategory	Query by ATC classifications or WHO DD preferred names
Antipsychotics	1 st gen./typical antipsychotics	N05AA Phenothiazines with aliphatic side-chain, N05AB Phenothiazines with piperazine structure, N05AC Phenothiazines with piperidine structure, N05AD Butyrophenone derivatives, N05AF Thioxanthene derivatives, N05AG Diphenylbutylpiperidine derivatives  WHO DD preferred names: - CALCIUM CARBONATE;DIMETICONE;HALOPERIDOL;L ITHIUM;SODIUM BICARBONATE;TARTARIC ACID
	2 nd gen./atypical antipsychotics	N05AE Indole derivatives, N05AH Diazepines, oxazepines, thiazepines and oxepines, N05AL Benzamides, N05AX Other antipsychotics WHO DD preferred names: - BLONANSERIN
Benzodiazepines (or derivatives)		N03AE Benzodiazepine derivatives, N05BA Benzodiazepine derivatives,

		N05CD Benzodiazepine derivatives, N05CF Benzodiazepine related drugs	
Anticholinergics		N04A Anticholinergic agents	
Antiepileptics (excluding any benzodiazepines or derivatives)		N03 Antiepileptics, excluding N03AE Benzodiazepine derivatives	
	Selective Serotonin Reuptake Inhibitors (SSRIs)	N06AB Selective serotonin reuptake inhibitors	
	Serotonin- Norepinephrine Reuptake Inhibitors (SNRIs)	WHO DD preferred names:  - DESVENLAFAXINE - DULOXETINE - DULOXETINE;MECOBALAMIN - ESREBOXETINE - LEVOMILNACIPRAN - MILNACIPRAN - VENLAFAXINE	
Antidepressants	Monoamine Oxidase Inhibitors (MAOIs)	N06AF Monoamine oxidase inhibitors, non-selective, N06AG Monoamine oxidase A inhibitors  WHO DD preferred names: - BIFEMELANE - MINAPRINE - SELEGILINE	
	Tricyclic antidepressants (TCAs)	N06AA Non-selective monoamine reuptake inhibitors  WHO DD preferred names:  - NITROXAZEPINE  - TIANEPTINE  Excluding the following WHO DD preferred names:  - CLOCAPRAMINE  - CLOMACRAN  - DICLOFENSINE  - LIAFENSINE  - MAPROTILINE  - NON-SELECTIVE MONOAMINE REUPTAKE INHIBITORS  - OXAPROTILINE	

Other	WHO DD preferred names:
antidepressants	- ACETYLCARNITINE;CHOLINE;CRATAEGUS
1	LAEVIGATA;GINKGO BILOBA;GLUTAMIC
	ACID;GRIFFONIA
	SIMPLICIFOLIA; THEOBROMA
	CACAO;TRAZODONE
	- ACETYLCARNITINE;CHOLINE;CRATAEGUS
	LAEVIGATA;GLUTAMIC
	ACID;OXITRIPTAN;THEOBROMA
	CACAO;TRAZODONE;VITIS VINIFERA
	- AGOMELATINE
	- AMIBEGRON
	- AMITIFADINE
	- ANSOFAXINE
	- APIMOSTINEL
	- BREXANOLONE
	- BUPROPION
	- BUPROPION;DEXTROMETHORPHAN
	- CITALOPRAM;MIRTAZAPINE
	- CUTAMESINE
	- EPTAPIRONE
	- ESKETAMINE
	- FLUPAROXAN
	- GEPIRONE
	- LIAFENSINE
	- MAPROTILINE
	- MIANSERIN
	- MIRTAZAPINE
	- NEFAZODONE
	- NOMIFENSINE
	- OXAPROTILINE
	- PRAZITONE
	- RAPASTINEL
	- REBOXETINE
	- RISLENEMDAZ
	- SETIPTILINE
	- TRAZODONE
	- VERUCERFONT
	- VILAZODONE
	- VILOXAZINE
	- VORTIOXETINE
	- ZELQUISTINEL
	- ZURANOLONE

